PMM	Pattern mixture model
PPS	Per protocol set
SADE	Serious adverse device effect
SAE	Serious adverse event
SAP	Statistical analysis plan
SAS	Statistical analysis system
SD	Standard deviation
SOC	System organ class
VAS	Visual analog scale
WHO-DDE	World Health Organization Data Dictionary Extended

## 1. INTRODUCTION

This Statistical Analysis Plan (SAP) outlines the statistical methods for the display, summary and analysis of data collected within the scope of protocol GM-11, dated 2015-10-13. The purpose of this plan is to provide general guidelines from which the analysis will proceed.

The SAP should be read in conjunction with the study protocol and the electronic Case Report Forms (eCRFs). This version of the SAP has been developed using the final version of the protocol mentioned above and the final version of the annotated eCRFs dated 22-APR-2015.

electroCore® has designed a non-invasive vagus nerve stimulation (nVNS) device called gammaCore-R®. gammaCore-R® is a hand-held, battery-powered unit that produces a proprietary electrical waveform in the vicinity of the vagus nerve in the neck. Each dose is relatively brief (120 seconds) and the user maintains control over the stimulation intensity.

The post-marketing clinical follow-up study will collect further clinical data related to the extended safety and efficacy of nVNS with gammaCore-R® for the preventive treatment of episodic migraine.

## 2. STUDY OBJECTIVES

### 2.1 Primary Objective

The primary objective is the difference between the gammaCore®-R and the sham treatment groups in mean reduction in number of migraine days during the last four weeks in the twelve-week randomized period compared with the four week run-in period.

### 2.2 Secondary Objectives

The secondary objectives are:

- To evaluate the rate of responders for the gammaCore®-R group compared to the sham group. A responder is defined as recording at least 50% reduction in migraine days during the last four weeks in the twelve-week randomization period compared to the four week run-in period.
- To evaluate the difference between the gammaCore®-R and sham treatment groups in mean reduction in number of headache days during the last four weeks in the twelve-week randomized period compared to the four week run-in period.
- To evaluate the difference between the gammaCore®-R and the sham treatment groups in the mean reduction in acute headache medications taken during the last four weeks in the twelve-week randomized period compared to the four week run-in period.
- Compare improvement in headache disability using Headache Impact Test-6 (HIT-6)
- Compare improvement in Migraine Disability Assessment (MIDAS)
- Compare Quality of Life EQ-5D-5L
- Reduction of number of headache/migraine days in the open label period compared to baseline run-in period and the randomized period

- Adverse events

### 2.3 Other Objectives

[figure not shown]
- Blinding questions
- Subject satisfaction question; and
- Ease of use

## 3. STUDY DESIGN

### 3.1 Study Design

This is a prospective, randomized, sham-controlled, multi-center investigation designed for comparison of two parallel groups, gammaCore®-R (active treatment) and a sham (inactive) treatment. The study period will begin with a four week run-in period, during which there is no investigational treatment. The purpose of the run-in period will be to establish the baseline for comparisons. The run-in period will be followed by a 12 week randomized period when the subjects will be randomized (1:1) to either active treatment or sham (inactive) treatment. Figure 1 graphically displays the study design.

The randomized period will be followed by a 24 week open label period, where the subjects in the sham treatment group will switch treatment assignment and receive a gammaCore®-R device and the gammaCore®-R group will continue to receive an active treatment (See Protocol Section 7.1 for details).

**Figure 1: Diagram of Study Design**

### 3.2 Randomization

Subjects will be randomized to either the active treatment arm or sham control arm (allocation 1:1) under a randomized variable block design, stratified by study site.

Subjects will be randomized using Merge eClinical OS Interactive Web Response system (IWRS) via computer key board data entry for a web based interface.

The site personnel (the investigator or his designee) will enter the required study and subject information and will then be provided with a subject randomization number and device serial number. Once subject numbers, serial numbers, and randomization numbers have been assigned, they cannot be reassigned.

The IWRS will provide the site personnel confirmation of the randomization number and device serial number assigned to each subject.

A sponsor designee will also have a copy of the randomization schemes for each study site and will be responsible for providing the un-blinded trainer with the randomization schemes.

### 3.3 Hypothesis Testing

Let  $\mu_{\text{Active}}$  be the mean change (from the 4-week run-in period) in the number of migraine days for the active treatment group and  $\mu_{\text{Sham}}$  be the mean change in the number of migraine days for the sham treatment group. Then the effectiveness of the gammaCore®-R device can be measured by testing the difference in mean changes,  $\mu_{\text{Active}} - \mu_{\text{Sham}}$ . The null and alternative hypotheses of interest are:

$$H_{\text{null}}: \mu_{\text{Active}} - \mu_{\text{Sham}} = 0 \text{ versus } H_{\text{alt}}: \mu_{\text{Active}} - \mu_{\text{Sham}} \neq 0$$

### 3.4 Interim Analysis

The analysis of the primary and secondary efficacy endpoints will occur after all subjects have completed the randomized/controlled period and their data is deemed clean; and, before the formal completion of the study (at the end of the open-label period). As this is the final analysis for the primary objective of the study, no adjustment of alpha will be performed.

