#### 7.4.2 Secondary Endpoints

##### *Percentage Reduction in Migraine Days and Responder Rate*

The percentage reduction in migraine days from the run-in period and achievement of 50% reduction in migraine days during the last 4 weeks of the randomized period are two secondary endpoints. Percentage reduction in migraine days is calculated as:

$$\text{Percentage Reduction} = -100 \times (\text{Change}_{\text{Run-in}} / \text{Run-in Value})$$

Using this value, an indicator of achievement of 50% reduction during the last 4 weeks of the randomized period can be defined as:

Response = 1 (Yes) if Percentage Reduction  $\geq 50\%$

Response = 0 (No) if Percentage Reduction is non-missing and  $< 50\%$

The number of migraine days, the change from run-in, and the percentage change from run-in to the open-label period will also be calculated. This will be completed for Month 3 and Month 6 of the OL period. For

$$\text{Month 3 OL Value} = \sum_{i=1}^{84} \text{Day } i, \text{ where Day } i = 1 \text{ (had a migraine)}$$

In the event that a subject does not have at least 70 days in the OL period the following rules will be used to calculate the Month 3 OL value:

1. If the number of study days in the OL period is less than 70, the month 3 OL value will not be calculated, but rather imputed to the DB value (and thus resulting in a  $\text{Change}_{\text{OL3}} = \text{Change}_{\text{Run-in}}$ , implying no change between the 3 month DB and 3 month OL periods).

$$\text{Month 3 OL Value} = \text{Month 3 (DB) Value}$$

2. If number of study days in the OL period is greater than or equal to 70, but less than 84, the month 3 OL value would be calculated as:

$$\text{Month 3 OL Value} = \sum_{i=1}^z \text{Day } i, \text{ where Day } i = 1 \text{ (had a migraine)}$$

where  $z$  represents the subject's last day (within 84 days) of participation in the OL period with diary data present.

To ensure consistency of this value for all subjects, the value will be adjusted to reflect an estimated number of days with migraine per 28 day interval. For example, if a subject records data for  $x$  days out of 28 days and have  $y$  days with migraine, then the adjusted number of days with migraine in 28 days is  $(28/x)*y$ , with a maximum value of 28.

Then the change from Run-in is calculated using the adjusted values as:

$$\text{Change}_{\text{OL3}} = \text{Month 3 OL value} - \text{Run-In value}$$

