$$\text{Month 6 OL Value} = \sum_{i=141}^{168} \text{Day } i, \text{ where Day } i = 1 \text{ (had a migraine)}$$

In the event that a subject does not have at least 154 days in the OL period the following rules will be used to calculate the Month 6 value:

1. If the number of study days in the OL period is less than 154, the month 6 OL value will not be calculated, but rather imputed to the Month 3 OL value (and thus resulting in a  $\text{Change}_{\text{OL6}} = \text{Change}_{\text{OL3}}$ , implying no change between the 6 month OL and 3 month OL periods).

$$\text{Month 6 OL Value} = \text{Month 3 OL Value}$$

2. If number of study days in the OL period is greater than or equal to 154, but less than 168, the month 6 OL value would be calculated as:

$$\text{Month 6 OL Value} = \sum_{i=1}^z \text{Day } i, \text{ where Day } i = 1 \text{ (had a migraine)}$$

where  $z$  represents the subject's last day of participation (within 168 days) in the OL period with diary data present.

To ensure consistency of this value for all subjects, the value will be adjusted to reflect an estimated number of days with migraine per 28 day interval. For example, if a subject records data for  $x$  days out of 28 days and have  $y$  days with migraine, then the adjusted number of days with migraine in 28 days is  $(28/x)*y$ , with a maximum value of 28.

Then the change from Run-in is calculated using the adjusted values as:

$$\text{Change}_{\text{OL6}} = \text{Month 6 OL value} - \text{Run-In value}$$

Results will be stratified by randomized treatment group.

In addition, the change from the double-blind period to 3 and 6 months of the open label period will be calculated or derived in the same manner for the comparison of the run-in to double-blind, randomized phase. Results will be stratified by randomized treatment group. For the calculation of percent change from the double-blind period to each of the open label periods, if there were zero migraine days at the double-blind period, percent reduction will be imputed as 100%.

$$\text{Change}_{\text{OL3DB}} = \text{Month 3 OL value} - \text{Month 3 value}$$

$$\text{Change}_{\text{OL6DB}} = \text{Month 6 OL value} - \text{Month 3 value}$$

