## 8.4.2 Secondary Efficacy Analyses

### Responder Rate

The number and percentage of subjects with at least a 50% reduction in migraine days will be summarized by device group, for each study phase (DB, 3 month OL, 6 month OL). The difference between the two device groups in will be compared using a two-sided, 95% CI (active minus sham). The p-value will be calculated using Fisher's exact test. If the p-value from the resulting exact test is <0.05, then the null hypothesis will be rejected.

As a sensitivity analysis, for responder rate in the DB phase, the two treatment groups will be compared using logistic regression analyses with an indicator for achieving at least a 50% reduction in migraine days (0 indicates no, 1 indicates Yes [event]) as the dependent variable and treatment group and center as fixed effects with number of migraine days in the 4-week run-in period as a covariate and again with treatment group, center, and aura as fixed effects with number of migraine days in the 4-week run-in period as a covariate.. The adjusted proportions, odds ratio, and 95% CIs f will be reported.

In addition, summary statistics and two-sided 95% CI will be produced for the following secondary effectiveness outcome measures and compared between the two treatment groups:

- The percentage reduction in migraine days during each time period (DB, 3 month OL, and 6 month OL) compared to the run-in period.
- The number of headache days during each time period (Run-in, DB, 3 month OL, and 6 month OL) as well as the change in number of headache days from the four week run-in period.
- The number of days in which acute headache medications were used during each time period (Run in, DB, 3 month OL, and 6 month OL); and, the change in the number of days from run-in.
- Scores at each visit and change in quality of life from run-in to each assessment as measured by the EQ-5D-5L, HIT-6, and MIDAS.

In addition, similar summaries may be produced for change in outcomes reported from the end of the DB period to assessments in the OL period.

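### SAP 3.4 times the secondary efficacy analysis before the open-label period ends without excluding the open-label endpoints, so the day-count fill rules would treat subjects still in follow-up as withdrawn

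*SAP*

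**What the plan says.** **Timing.** SAP 3.4 states: "The analysis of the primary and secondary efficacy endpoints will occur after all subjects have completed the randomized/controlled period". It adds that the data must be clean and that the analysis precedes study completion, which it places at the end of the OL period. Its reason for leaving alpha alone is: "As this is the final analysis for the primary objective of the study, no adjustment of alpha will be performed".

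**OL outcomes are secondary.** Section 2.2 lists among the secondary objectives: "Reduction of number of headache/migraine days in the open label period compared to baseline run-in period and the randomized period". Section 7.4.2, headed as secondary endpoints, defines migraine days, change and percentage change for the OL period: "This will be completed for Month 3 and Month 6 of the OL period". Section 8.4.2 summarises the responder rate and the other diary outcomes for the double-blind phase and for OL Months 3 and 6.

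**Fill rules in 7.4.2.** For Month 3: "If the number of study days in the OL period is less than 70, the month 3 OL value will not be calculated"; the double-blind value is used instead. For Month 6: "If the number of study days in the OL period is less than 154, the month 6 OL value will not be calculated"; the OL Month 3 value is used instead.

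**The concern.** The 3.4 cut falls while some subjects are still in the 24-week (168-day) OL period. The fill rules look only at how many OL days a subject has, not at whether the subject has left. A subject who has simply not yet reached OL Day 154 is therefore handled like a dropout.

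The rules also chain. With under 70 OL days, OL Month 3 takes the double-blind value and OL Month 6 then takes that same value. For a subject randomized to sham, a count from the sham period would be reported as a Month 6 result on the active device, with a change from double-blind of exactly zero. That would dilute the comparison of OL with the randomized period named in 2.2. It would also carry any double-blind difference between groups into a phase in which both groups use the active device.

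**Working it through.** **1. The sections side by side.**
- 3.4 covers the primary and secondary efficacy endpoints at one time, before the OL period ends, and makes no exception.
- 2.2, 7.4.2 and 8.4.2 place OL Months 3 and 6 among the secondary outcomes.
- No section gives a separate time for the OL analysis. Section 4 speaks of a single database lock.
- The missing-data sensitivity analyses in 8.4.1 concern values imputed under 7.4.1. The complete-population analysis in 8.4.3.5 requires non-imputed data only for the run-in and double-blind periods. Neither covers OL fills. Section 8.1 does flag imputed values in the analysis dataset, so they could be identified, but they would still be analysed.

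**2. Share of subjects filled only because of the cut.** The SAP has no figure to reproduce here, since it gives neither accrual duration nor cleaning time. Both are assumed.

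Inputs from the SAP: thresholds of 70 and 154 OL days (7.4.2); OL length 24 × 7 = 168 days (3.1).

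Assumptions: uniform entry over *R* days; no withdrawals; the cut comes *L* days after the last subject enters OL. A subject who entered OL *u* days before the last one has *u* + *L* OL days at the cut, with *u* uniform on 0 to *R*. For threshold *D*:

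share below threshold = max(0, (*D* − *L*) / *R*)

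OL Month 6 filled (*D* = 154):

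| Lag *L* | *R* = 183 (6 months) | *R* = 365 (12 months) | *R* = 548 (18 months) |
|---|---|---|---|
| 30 | 124/183 = 68% | 124/365 = 34% | 124/548 = 23% |
| 60 | 94/183 = 51% | 94/365 = 26% | 94/548 = 17% |
| 90 | 64/183 = 35% | 64/365 = 18% | 64/548 = 12% |

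Double-blind value used for OL Month 3, and hence for Month 6 (*D* = 70):

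| Lag *L* | *R* = 183 | *R* = 365 | *R* = 548 |
|---|---|---|---|
| 30 | 40/183 = 22% | 40/365 = 11% | 40/548 = 7% |
| 60 | 10/183 = 5.5% | 10/365 = 2.7% | 10/548 = 1.8% |
| 70 or more | 0 | 0 | 0 |

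**3. When the problem disappears.** No Month 6 value is filled because of the cut only if *L* is at least 154, that is, if the cut falls within the last 168 − 154 = 14 days of the last subject's OL period. Any earlier cut fills some subjects still in follow-up. The double-blind carry-over is narrower: it needs a lag under 70 days.

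**The case against.** The strongest reply is that 3.4 is meant only for the randomized-period endpoints. It is headed as an interim analysis, and its requirement that the data be clean most naturally refers to the period just completed, since OL data cannot be clean while OL is running. On that reading OL results follow at study end, and the protocol, which is not at hand, may say so. This is plausible and may well be the intention. It is not what the SAP states, however, and if it is right the SAP gives no time at all for the OL analysis. Both readings call for the same correction.

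Three stronger readings are tempting, and the SAP does not support them:
- **Inflated type I error from an unadjusted early look.** This needs a second test of the same OL endpoints at study end, and none is stated. With a single analysis there is no repeated look.
- **A significance rule for every OL outcome.** The p < 0.05 rule in 8.4.2 is given for the responder rate, by Fisher's exact test. The other OL diary and questionnaire outcomes get summaries and 95% confidence intervals. The OL objective in 2.2 is a comparison with run-in and the randomized period.
- **Certain contamination by double-blind values.** This depends on the cleaning lag and vanishes at 70 days or more. Month 6 would then be filled only from actual OL Month 3 data.

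**Conclusion.** The point holds as a timing and scope error in 3.4 combined with fill rules in 7.4.2 that do not separate ongoing from withdrawn subjects. The text is wrong as written, and the severity is minor. Followed literally, it replaces OL Month 6 values that are still to come for roughly an eighth to two thirds of subjects, over lags of 30 to 90 days and entry over 6 to 18 months. Those shares rest on assumed uniform entry and an assumed lag, and should be recalculated from the actual accrual. The primary endpoint, its unadjusted alpha (for which the reason in 3.4 is sound) and the randomized-period secondary endpoints are not affected.

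**What to change.** - **3.4:** limit this analysis to the primary efficacy endpoint and the secondary efficacy endpoints of the randomized period. State that every endpoint using OL data (OL Month 3, OL Month 6, change from double-blind, and the OL questionnaires) is analysed once, after the last subject has completed or left the OL period and those data are locked.
- **7.4.2:** apply the under-70-day and under-154-day fill rules only to subjects who have left the OL period. State that any OL figures shown at the earlier analysis are descriptive and use observed values only.

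The cost is two or three sentences. OL results wait until study end; no subjects or procedures are added.

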### 3.5 Sample Size

Table 1 provides the required sample size per treatment group when the number of migraine days per 28-day period is used as the primary outcome measure. Sample size calculations are based on the clinically meaningful difference between active and sham treatment groups in change from baseline. Assuming a type I error of 5% (two-sided) and 90% power, Table 1 displays the required sample sizes for different values of the common standard deviation (2.0, 2.5, 3.0 and 3.5) and the presumed difference between treatment groups (1, 1.5 and 2 days). Selecting an improvement of 1 day and a common standard deviation of 2.5 requires 133 subjects per treatment group. With 15% drop-out during the randomized treatment period, a total of 160 subjects per treatment group (or 320 subjects total) would need to be randomized.

**Table 1: Required Sample Size per Treatment Group  
Assuming Type I Error ( $\alpha$ ) = 5% (two-sided) and 90% Power**

Variability (Common SD*, $\sigma$ )	Clinically Significant Improvement: Active – Sham = $\Delta$		
	1-day	1.5-day	2-day
2.0	86	--	--
2.5	133	60	34
3.0	191	86	49
3.5	259	115	66

\*Estimated standard deviation for change from baseline. Standard deviations for baseline and post treatment scores are between 2.0 to 3.5.

### **3.6 Study Procedures**

Procedures and outcome measures will be collected as described in the clinical investigation flow chart shown in Table 2.

**Table 2. Clinical Investigation Flow Chart**

Period	Run-in	Randomized					Open label					
Visit number	V1	V2	V3*	V4	V5 **	V6	V7 *	V8	V9**	V10	V11	V12
Week	-4	0	1	4	8	12	13	16	20	24	30	36
Day	-28	1+/-3	7+/-3	28+/-3	56 +/- 5	84 +/-5	91 +/-3	112 +/- 3	140+/-5	168+/-5	210 +/-5	252+/-5
Signed Consent Form	✓											
Randomization		✓										
Demographics	✓											
Inclusion/Exclusion criteria	✓											
History of migraine	✓											
Medical and surgical history	✓											
Physical examination	✓											
ECG	✓											
Urine pregnancy test 	✓											
Blood pressure and weight	✓					✓						✓
HIT-6 		✓		✓	✓	✓	✓	✓	✓	✓		✓
EQ-5D-5L 		✓		✓	✓	✓	✓	✓	✓	✓		✓
MIDAS 		✓				✓				✓		✓
Subject satisfaction question						✓						✓
Easy to use question						✓						✓
Blinding question			✓			✓						
Device training and placement		✓		✓		✓						
Collect device/ gammaCore®-R						✓						✓
Diary completion	✓	✓	✓	✓	✓	✓	✓	✓	✓	✓	✓	✓
Concomitant medication	✓	✓	✓	✓	✓	✓	✓	✓	✓	✓	✓	✓
Adverse Event 		✓	✓	✓	✓	✓	✓	✓	✓	✓	✓	✓
Study Termination												✓

 Fertile woman only.

 All new events during the run-in will be reported under adverse events.

Call\* - One week after the previous visit.

Call \*\*- One month after the previous visit.

 At visit 2 and 6 these questionnaires will be completed by the subjects on paper forms during the visit.

## 4. DATA AND ANALYTICAL QUALITY ASSURANCE

The study endpoints and analytic approaches are both prospectively defined and documented in the protocol and in this SAP. The SAP will be finalized, and protocol violations will be identified and decisions for inclusion and exclusion of subjects from the per-protocol analysis population will be made prior to the database lock, unblinding, and data analysis.

## 5. ANALYSIS POPULATIONS

Subjects screened but not included in the study will not be presented in any listings or tables. Subjects that enter Run-in but do not meet criteria for randomized will be accounted for in tables, and their data will be provided in listings.

### 5.1 Intent-to-Treat (ITT) Population

The Intention to treat (ITT) population includes all randomized subjects with at least one verified treatment post-training during the 12 week randomized period. The ITT population will be analyzed using the subject's randomized treatment regardless of which treatment the subject actually received.

The ITT is considered the primary analysis dataset, and will be used for all primary and secondary efficacy analyses.

### 5.2 Per Protocol (PP) Population

The per protocol (PP) population includes all ITT subjects who received the correct treatment with no major protocol deviations which could affect the assessment of efficacy. Major protocol deviations include, but are not limited to, the following:

- The subject did not reach visit 6
- Less than 67% compliance with treatment per month in the randomized period (refer to section 6.3).

The final criteria for the PP population, regarding which protocol deviations warrant exclusions, will be determined when all data on protocol deviations are available and before breaking the blind.

If the difference in sample size between the ITT and PP populations is more than 5%, then the primary efficacy analyses will be repeated in the PP population.

